12.3 END OF STUDY	20
13 REPORTING, PUBLICATIONS AND NOTIFICATION OF RESULTS.....	21
13.1 AUTHORSHIP POLICY	21
13.2 PUBLICATION.....	21
13.3 PEER REVIEW.....	21
14 REFERENCES.....	21

PROTOCOL APPROVAL

Longer term impact of COVID 19 infection in people with diabetes

Signatures

The undersigned confirm that the following protocol has been agreed and approved by the Sponsor and that the Chief Investigator agrees to conduct the study in compliance with this approved protocol and will adhere to the principles of GCP, the Sponsor SOPs, and any other applicable regulatory requirements as may be amended from time to time.

[name]
Chief Investigator

Signature

Date

[INSERT PI NAME]
[INSERT HEALTH BOARD
SITE NAME]
Principal Investigator

Signature

Date

LIST OF ABBREVIATIONS

AE	Adverse Event
BG	Blood Glucose
CI	Chief Investigator
CNORIS	Clinical Negligence and Other Risks Indemnity Scheme
COVID-19	Coronavirus SARSCOV-2
CRF	Clinical Research Facility
DMS	Data Management System
GCP	Good Clinical Practice
ICF	Informed Consent Form
NHS GGC	NHS Greater Glasgow and Clyde
ISF	Investigator Site File
NRS	NHS Research Scotland
PI	Principal Investigator
REC	Research Ethics Committee
SDG	Scottish Diabetes Group
SOP	Standard Operating Procedures
SMF	Study Master File

SUMMARY/SYNOPSIS

Study Title	Longer term impact of COVID 19 infection in people with diabetes (Short Title: Diabetes Long COVID study)	
Study Design	Observational Case Cohort study with Nested Case Control study	
Study Population	Adults with Type 1 and Type 2 Diabetes in Scotland	
Sample Size	Total sample size in Nested Case Control study, as per IRAS form: 1000 participants (500 cases and 500 matched controls, with at least 200 people in each of the categories of Type 1 and Type 2 diabetes)	
Planned Study Period	May 2021 to approximately October 2022	
Follow up phase duration	1 year (cases only)	
Aims	To understand the proportion of people with diabetes who experience longer term symptoms or illness after covid-19 infection, the nature of these symptoms, and the potential health impact of that.	
Primary	Objective: Case Cohort: After COVID infection, what proportion of people with type 1 and type 2 diabetes experience symptoms in the longer term (up to 18-24 months after index infection)?	Outcome Measures: The prevalence of symptoms in the longer term in people with diabetes up to 2 years after COVID-19 infection using Wellcome questionnaire

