3 STUDY OBJECTIVES & OUTCOMES

To understand the proportion of people with diabetes who experience longer term symptoms or illness after COVID-19 infection, the nature of these symptoms, and the potential health impact of that.

The primary objectives of the study are:

After COVID infection, what proportion of people with type 1 and type 2 diabetes experience symptoms in the longer term (up to 18-24 months after index infection)?

The secondary objectives of the study are:

What is the impact of “long COVID” upon physical activity, diabetes control and outcomes?

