7.2 PROPOSED ANALYSES

An analysis plan will be prepared for the University of Glasgow Research Data Management department before the study closes, to detail what analysis will be performed on the data.

Case cohort study:

This includes **participant completed questionnaires only**. We will not have access to clinical record for whole group (limited to those in nested study) and will rely on patient self-report of COVID testing and infection to create groups. Analysis will be in three groups:

- a. Test positive COVID declared (**cohort A**)
- b. no test but self-declared COVID (**cohort B**)
- c. no COVID infection declared, including those with suspected infection but test negative (**control**)

Analysis of this data will include

1. **Frequency of COVID symptoms** (derived from question 1.3 Wellcome questionnaire: 28 domains answering yes/no for 0-28 score and by self-report at time of infection at 3 months and current (>3 months)).
 - a. **Primary analysis:** current score cohort vs control with adjustment for limited demographic panel: age band, ethnicity, sex, type of diabetes
 - b. Secondary analyses:
 - i. within cohort comparison of time of infection vs 3 months vs current
 - ii. comparison time of infection and 3 months vs current score of control (with adjustment)
2. **Other questionnaire data:** diabetes depression score, DQOL all of which are assessed currently only and will be assessed in cohort vs control.
3. Comparison of above end points in cohort B to cohort and controls.

NESTED CASE CONTROL STUDY

For this data, consent will allow access to confirm that patient is COVID test positive in the clinical record. Definitions and comparison will therefore be between:

Cases - COVID test positive in clinical record

Control - no previous clinical COVID infection reported by patient, no record positive COVID test.

Case vs control (First visit)

1. **Frequency of COVID symptoms** (derived from question 1.3 Wellcome questionnaire: 28 domains answering yes/no for 0-28 score and by self-report at time of infection at 3 months and current (>3 months)).
 - a. **Primary analysis:** current score case vs control with adjustment for age, sex, ethnicity, sex, type of diabetes, SIMD
 - b. Secondary analyses:
 - i. within cohort comparison of time of infection vs 3 months vs current
 - ii. comparison time of infection and 3 months vs current score of control (with adjustment)
 - iii. relationship of cycle threshold to symptom scores

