2. **Other questionnaire data:** diabetes depression score, DQOL all of which are assessed currently only and will be assessed in cohort vs control
3. **Walk test**
4. **Hand grip**
5. **Pulmonary function measures eg. FEV1**

Comparison of cases vs COVID positive cohort for demographics and main study measures.

Case vs control (First and second visit data)

1. **Frequency of COVID symptoms** (derived from question 1.3 Wellcome questionnaire: 28 domains answering yes/no for 0-28 score and by self-report at time of infection at 3 month, at time of first questionnaire, first visit and at second visit).
 - a. **Primary analysis:** second visit score case vs control (first visit) with adjustment for age, sex, ethnicity, sex, type of diabetes, SIMD
 - b. Secondary analyses:
 - i. within cohort comparison of time of infection vs all time points
 - ii. comparison time of infection and 3 months vs current score of control (with adjustment)
2. **Other questionnaire data:** diabetes depression score, DQOL all of which are assessed first and second visit cohort vs control (first visit)

3. **Walk test** first and second visit cohort vs control (first visit)
4. **Hand grip** first and second visit cohort vs control (first visit)
- Pulmonary function measures eg. FEV1** first and second visit cohort vs control (first visit)

B. Screening log. As above contain patient identifiers, will be held on NHS computers.

Output - acceptance rate for study

C. Study data - will be held within Redcaps platform. Outputs: process data on completion of the different modules of the study, final study dataset.

Key aspects will be

- a. Record of consent and electronic consent
- b. Ability to enter data to personal computer/ smartphone by participant
- c. Ability to enter separate data under same study ID for study visit
- d. Cloud exportable to SAS/ SPSS/ R

Analyses will be carried out by the study team using the statistical support offered by the University of Glasgow.

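### The primary objective is a proportion with longer-term symptoms, but the primary analysis compares a 0-28 score with controls and no listed analysis gives a proportion

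*Protocol*

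**What the plan says.** Section 3 of the protocol asks: "After COVID infection, what proportion of people with type 1 and type 2 diabetes experience symptoms in the longer term", with a horizon of up to 18-24 months after the index infection. The synopsis gives the matching outcome measure: "The prevalence of symptoms in the longer term in people with diabetes up to 2 years after COVID-19 infection using Wellcome questionnaire". Both belong to the case cohort (online questionnaire) study. The synopsis places the nested case control study under the secondary objective.

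Section 7.2 derives the symptom variable from question 1.3 of the Wellcome questionnaire: "28 domains answering yes/no for 0-28 score", recorded for the time of infection, 3 months and currently (more than 3 months). Three analyses are then labelled primary, each under its own heading:

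- Case cohort study: "current score cohort vs control with adjustment for limited demographic panel: age band, ethnicity, sex, type of diabetes".
- Nested study, first visit: "current score case vs control with adjustment for age, sex, ethnicity, sex, type of diabetes, SIMD".
- Nested study, first and second visit data: "second visit score case vs control (first visit) with adjustment for age, sex, ethnicity, sex, type of diabetes, SIMD".

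The secondary analyses of the same item are comparisons too, for example "within cohort comparison of time of infection vs 3 months vs current".

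**The concern.** The objective asks how many people have symptoms. The analysis named to answer it asks how much higher the average symptom count is than in controls, after adjustment. These are different quantities. Diabetes type, which the objective names, enters only as an adjustment covariate, so the primary analysis gives no result by type. The time frames differ as well: the objective looks up to 18-24 months after infection, while the analysis uses current symptoms at any point beyond 3 months.

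A team that followed Section 7.2 as written would report an adjusted score difference and would still lack the figure the study was set up to give. Someone would then have to choose a cut-off for having symptoms after seeing the data. With 28 items, many of them common in diabetes without COVID-19, the reported prevalence could depend heavily on that choice.

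**Working it through.** **1. Objective against analysis.**

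- Quantity: a proportion (synopsis, Section 3); an adjusted score comparison (Section 7.2, all three analyses labelled primary).
- Diabetes type: named in the question; a covariate in the analysis.
- Rule for having symptoms: required by a prevalence; none is given. Section 7.1 says only that long COVID definitions are still evolving.
- Time: up to 18-24 months, or 2 years in the synopsis outcome; current, more than 3 months, in Section 7.2.

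Nothing listed in Section 7.2, primary or secondary, is an estimated proportion with symptoms.

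**2. The plan's own sample size figures (Section 7.1).** For two means, n per group = 2(z_0.975 + z_0.90)² / d², taking alpha 0.05 as two-sided.

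- d = 0.2: 2 × (1.960 + 1.282)² / 0.04 = 525.4, so 526. This reproduces the stated 526.
- d = 0.5: 2 × (1.960 + 1.282)² / 0.25 = 84.1, so 85. This reproduces the stated 85.
- At the planned 500 per group, power is 88.5% for 0.2 SD, 89.0% for 50% against 40%, and 93.3% for 20% against 12%.

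The arithmetic is sound, but every figure concerns a between-group difference. None describes the precision of a prevalence.

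**3. Does a mean score fix a prevalence?** The protocol gives no expected mean; assume 3 for illustration.

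- Exact limits on a 0-28 scale: the share with at least one symptom is smallest when those affected all score 28, 3/28 = 10.7%, and largest when everyone scores 3, 100%.
- Smoother shapes: for a negative binomial with mean m and dispersion k, P(at least 1) = 1 − (k/(k + m))^k. With m = 3:
  - k = 0.3: 51%
  - k = 0.5: 62%
  - k = 1: 75%
  - k = 3: 88%
  - Poisson limit, 1 − e^(−3): 95%

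The same mean is compatible with very different prevalences, so the objective's figure cannot be recovered from the score comparison. The negative binomial has no upper bound at 28, so these shares are approximate.

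**4. Precision if a prevalence were estimated.** Half-width of the 95% CI = 1.96 × √(p(1 − p)/n). At p = 50%:

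- n = 500 (nested case target): 1.96 × √(0.25/500) = 4.4 points.
- n = 200 (nested minimum per diabetes type): 1.96 × √(0.25/200) = 6.9 points.
- n = 100 (minimum cases at end of study, Section 12.3): 1.96 × √(0.25/100) = 9.8 points.

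At p = 20% the three are 3.5, 5.5 and 7.8 points. They are illustrative only: these sizes belong to the nested study, and the protocol gives no target size for the online cohort, to which the primary objective belongs.

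**The case against.** The best defence is that the item is headed as a frequency of symptoms, is built from yes/no answers, and sits in a list that is not closed, with an analysis plan to follow. A cut-off is ordinary content for such a plan, and prevalence by type can be tabulated from data already collected. This stands as far as feasibility goes: the study can answer its question. It does not remove the conflict, because the protocol itself states the objective, the outcome and the primary analysis, and a later plan would have to depart from one of them.

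A second defence is that the control comparison is deliberate. Section 2 says that understanding the effects of COVID-19 depends on knowing the symptoms of the general diabetes population. That stands fully. An uncontrolled share with at least one of 28 symptoms would be hard to interpret alone, so the comparison should stay beside the prevalence.

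Third, separate estimates for the two types are not demanded in so many words. They are the natural reading, since the objective names both types and Section 4.10 sets a minimum of 200 of each among nested cases.

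A reader might also infer two stronger points that the document does not support:

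- That the primary analysis pools test-confirmed infection (cohort A) with untested self-declared infection (cohort B). Section 7.2 sets out three groups, and its item 3 compares cohort B with the cohort and with controls, so the cohort in the primary analysis reads as A and B is already shown separately.
- That three primary analyses inflate the false positive rate to 1 − 0.95³ = 14%. That needs independent tests. Here nested participants come from the questionnaire cohort, the score is the same throughout, and the second-visit analysis reuses the controls' first-visit data. Each label also heads its own dataset, and the synopsis already ranks the nested study as secondary.

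**Conclusion.** The point holds as a mismatch between the stated primary objective and the analysis named for it. Section 7.2 lists no analysis that estimates the proportion with longer-term symptoms, overall or by diabetes type, and no rule that defines it. The conclusion rests on the protocol's text and not on an arithmetic error; the sample size figures reproduce.

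The gap is material: at one assumed mean score, prevalence ranges from 51% to 95% across the shapes tried. That range depends on the assumed mean of 3 and the negative binomial form; the principle does not. It would go too far to say that the study cannot answer its question, or that the score comparison is wrong in itself. The precision obtainable in the online cohort cannot be stated from the document.

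**What to change.** In Section 7.2, name as the analysis of the primary objective the proportion of cohort A with current symptoms, by a binary rule on the question 1.3 items fixed before analysis (for example, at least one symptom). Report it with a 95% CI overall and separately for type 1 and type 2 diabetes, and show time since infection against the 18-24 month horizon. Beside it give the same proportion in controls and the adjusted risk difference, using the covariates already listed.

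Keep the adjusted 0-28 score comparison as a supporting analysis. Relabel the two nested-study primary analyses as the lead analyses of a secondary study, in line with the synopsis.

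The cost is protocol and analysis plan wording. The prevalence and the risk difference use yes/no items and demographics that are already collected. Reporting by time since infection needs an infection date, which the demographic panel in Section 6.2 does not list, so the team should confirm that the questionnaire captures it.

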People with diabetes are more likely to suffer severe adverse consequences of COVID-19 infection during the acute illness. In the Scottish population, people with diabetes are at considerably higher risk of having severe COVID-19 infection with odds ratio (OR) of fatal or critical care unit treated disease of 2.4 in type 1 diabetes and 1.4 in type 2 diabetes, with higher relative hazards in younger people with type 2 diabetes (4). Diabetes is also associated with an increased risk of in-hospital death following COVID in other populations (5). At this stage of the pandemic it is not clear whether there is also an increased susceptibility to longer term sequelae in people with diabetes. Risk scores have been developed to try to understand the likelihood of severe complications in acute illness both in diabetes (4) and the general population (6). Likelihood of longer term impact on health and economic factors will also be key in the public health response to COVID-19 and would ideally inform decisions as to the degree of shielding recommended for different groups of people in the population, including people with diabetes. Such information will also be key to the support of people with long-term consequences of COVID-19. Importantly however, chronic disease in general and diabetes and diabetes complications in particular, have well known effects on chronic wellbeing and association with depression, diabetes distress and related symptoms (7, 8). Understanding the effects of COVID in this population is therefore dependent on understanding the prevalence and architecture of symptoms in the *general* diabetes population.

In Scotland, information from clinical visits is held within the SCI Diabetes information system and, following additional data linkage to COVID-19 test results, this has allowed the detailed analysis of risks in the acute setting (4). We know that, to the end of July 2020, 2724 people with diabetes had had evidence of infection with COVID-19 (positive test, admission or death certificate) of whom 988 had unfortunately died. We expect therefore that conservatively there are at least 1736 people with diabetes in Scotland who may be living with the consequences of COVID-19. Understanding those consequences cannot be achieved with

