4.10 INCLUSION CRITERIA

Case cohort study (online questionnaires):

- Person with Diabetes (Type 1 or Type 2)
- Aged 18 or over
- Able to read and write in English

Nested case control study (CRF visits):

- Cases defined by positive COVID test in the clinical record. Cases will be invited sequentially from the cohort but will be selected to include at least 200 people in each of the diabetes subgroups (type 1 diabetes or type 2 diabetes).
- Controls defined by no positive COVID test in clinical records and no reported infection by participant. Controls will be matched after matching of a limited demographic panel available from the panel (age in 5 year bands, ethnicity, sex, type of diabetes, SIMD quintile).

All participants attending a research facility must have completed a COVID safety check before attending in person, in line with local guidance. Cases will be post-COVID and at least 10 weeks post positive test result.

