2. **From diabetes clinic lists or database search (SCI Diabetes):** To augment recruitment of COVID test positive participants we will also screen clinic lists and recruit directly. A member of the study team will screen diabetes clinic lists (eg trak or local clinical system, when possible SCI Diabetes) which routinely have a note of previous COVID infection. Name and CHI noted on screening log (excel spreadsheet held on NHS computer). If patient declines this is noted and no further action. If patient assents to contact then contact information taken (telephone and email – if neither possible postal address) and added to screening log. Electronic data collection link sent by preferred means. If electronic remote data collection not possible then paper questionnaires will be made available by post or study team will discuss over the phone. Cases identified to by SCI Diabetes search will be approached in writing with Caldicott Guardian approval in place within a Health Board (likely to be used in selected Health Boards only).
3. We will also advertise the study by leaflets and posters and via newsfeed to My Diabetes My Way, allowing self-referral to the study team.

NESTED CASE-CONTROL RECRUITMENT:

Cases, by definition, will have had a positive COVID test present on the clinical record. Potential cases will be selected from the cohort where a record of self-reported COVID infection is presented. Potential cases will be invited to CRF visit by telephone or email. Where assent is given by phone the clinical record will be checked to confirm positive COVID test, visit is arranged, and PIS sent. All other study procedures will take place only after face-to-face written consent is obtained at the CRF visit.

Controls will be selected from the pool of people who have completed the online questionnaire information and who have indicated that they have not had a **positive** COVID test and do not believe that they have had COVID infection. Those who had possible infection but subsequent test negative are included. Matching will be by age (5 year category),

ethnicity, sex, SIMD quintile and type of diabetes included in the participant completed questionnaire.

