6.2 DATA MANAGEMENT SYSTEM

We will use the RedCap data management system (DMS) hosted on a secure server at The University of Glasgow. This system will host all study information with the exception of screening logs and secure link between patient identifiers and study ID - both of which will be held separately on NHS computers. The RedCap platform allows for direct data entry by participants using either personal computer or smartphone.

Data held in NHS – on secure computer in CRF at each recruiting site:

Screening log for invitation to cohort from clinic lists – this will include patient identifiers restricted to CHI, name, telephone number, email address, as well as study process details (date contacted, consent given to send link for questionnaire data).

After written consent a separate file will be maintained with CHI and study ID.

Data held in RedCap (University of Glasgow)

All Cohort study information. This is entered by the participant and includes:

1. Panel of limited demographics (age in 5 year categories, ethnicity, sex, type of diabetes, duration of diabetes in 5 year categories, first 4 characters of post code to allow calculation of SIMD quintile)
2. Contact details (telephone, email address) – optional for participant
3. Study questionnaires (Wellcome, DQOL, DDS-1, EQ5D)

For nested case control study to this will be added:

1. Nested case control screening information recording interest in study/ willingness to attend CRF

After written consent at CRF the following will be added:

2. study ID
3. completed data from CRF visit (incremental walking, hand grip, pulmonary function, waist and thigh measurement, bioimpedence)
4. Participant information including (age to nearest year, ethnicity, sex, type of diabetes, diabetes duration), **e-mail address and/or contact telephone number**
5. Self filled questionnaire
6. Electronic pseudonymised linkage to variables in electronic clinical record being

- a. Sci-diabetes with measures of glycaemia (HbA1c), nephropathy, retinopathy, foot disease
 - b. SMR01 with data on hospital admissions
 - c. Where possible COVID test data for positivity and cycle threshold (cT)
- 7.

The DMS will be based on the protocol and case report form for the study and individual requirements of the investigators. The case report form will collect only information that is required to meet the aims of the study and to ensure the eligibility and safety of the participant.

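### The cohort primary comparison of symptom scores does not adjust for SIMD quintile, although the data to derive it are collected and the nested study both matches on it and adjusts for it

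*Protocol*

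**What the plan says.** Section 7.2 defines the cohort primary analysis as a comparison of the current symptom score between the infected cohort and the controls, "with adjustment for limited demographic panel: age band, ethnicity, sex, type of diabetes". The cohort control group is "no COVID infection declared, including those with suspected infection but test negative".

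Section 6.2 lists what every cohort participant enters. Besides age band, ethnicity, sex and type of diabetes, the panel holds "duration of diabetes in 5 year categories, first 4 characters of post code to allow calculation of SIMD quintile". Section 5.1 lists the same fields.

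For the nested study, section 4.10 matches controls on a "limited demographic panel available from the panel (age in 5 year bands, ethnicity, sex, type of diabetes, SIMD quintile", and section 5.1 matches on age category plus "ethnicity, sex, SIMD quintile and type of diabetes included in the participant completed questionnaire". The nested first-visit primary analysis is "current score case vs control with adjustment for age, sex, ethnicity, sex, type of diabetes, SIMD" (the repeated sex is a harmless slip). The nested second-visit primary analysis carries the same list, again with SIMD.

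On duration, the protocol says nothing beyond collecting it. Section 2 does state that "diabetes and diabetes complications in particular, have well known effects on chronic wellbeing" and connects them with depression, distress and related symptoms.

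**The concern.** The protocol treats deprivation as something that could distort a comparison of infected and uninfected people with diabetes: it matches on SIMD and then adjusts for it. In the comparison with no described matching step, it does neither.

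Imbalance in deprivation is plausible there. The cohort comes mainly from a research register of volunteers, but section 5.1 adds a clinic-list route intended to increase the number of test-positive participants. People reached through clinics need not resemble register volunteers. If deprivation also goes with more symptoms, or fewer, part of the adjusted difference in the 0-28 score would reflect who was recruited and not the infection. This matters because section 2 itself says that the effect of COVID can be understood only against the symptoms of the general diabetes population, which is what the control contrast supplies.

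**Working it through.** **Step 1. Set the variable lists side by side.**

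| Variable | Collected in cohort (5.1, 6.2) | Nested matching (4.10, 5.1) | Nested primary models (7.2) | Cohort primary model (7.2) |
|---|---|---|---|---|
| Age | yes (band) | yes (band) | yes | yes (band) |
| Sex | yes | yes | yes | yes |
| Ethnicity | yes | yes | yes | yes |
| Type of diabetes | yes | yes | yes | yes |
| SIMD quintile | yes, via part postcode | yes | yes | **no** |
| Diabetes duration band | yes | no | no | no |

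The demographic panel thus has three different contents: six items in 6.2, five in 4.10 (SIMD but not duration) and four in the cohort model (neither). SIMD is the only variable used in the nested study and left out of the cohort model.

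**Step 2. Is SIMD available for the cohort?** Yes. Section 6.2 gives its derivation as the purpose of the postcode field, and section 5.1 uses it to pick controls from people who have completed only the online questionnaire.

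**Step 3. Is the cohort balanced by design?** Section 1 calls the online study matched. Sections 4.10, 5.1 and 7.2 describe no matching for it: the control group is simply everyone who declares no infection. As planned, the comparison is unmatched.

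**Step 4. Can the bias be sized?** Not from the protocol. The formula is

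bias in SD of the score = g × d,

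where g is the shift in score associated with deprivation, given the other covariates, and d is the difference in the proportion deprived between the groups that remains after adjustment. Neither is given. Purely as an assumption, take g from 0.1 to 0.5 SD and d from 5 to 20 percentage points:

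- low: 0.1 × 0.05 = 0.005 SD
- middle: 0.3 × 0.10 = 0.03 SD
- high: 0.5 × 0.20 = 0.10 SD

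The sign could be either way. Unlike sampling error, this bias does not shrink as the cohort grows.

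**Step 5. The plan's own sample-size figures.** With two-sided 5% alpha (two-sidedness assumed) and 90% power, n per group = 2 × (1.960 + 1.282)² / δ². This gives about 525.4, so 526, at δ = 0.2 SD, and about 84.1, so 85, at δ = 0.5 SD. Both stated figures reproduce. They do not bear on the choice of covariates.

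**Step 6. What would adjustment cost?** SIMD quintile uses 4 degrees of freedom; duration bands would use perhaps 4 to 8 (assumed). With 1,000 participants and about 10 parameters already in the model (both assumed), the residual SD rises by a factor of √(990/986) = 1.002 for SIMD alone and √(990/978) = 1.006 for 12 extra degrees of freedom.

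**The case against.** Several counter-arguments have force.

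- **The primary objective is descriptive.** A reader might infer that the study's primary result is confounded. The synopsis and section 3 ask what proportion of people have symptoms after infection, and covariate adjustment does not touch that quantity. Only the comparative analysis in 7.2 is affected.
- **Duration is not an inconsistency.** A reader might put its omission on a par with that of SIMD. The protocol leaves duration out of the matching and out of every model, so it is consistent. Section 2 speaks of complications, not duration, and age band and type of diabetes may carry part of the same information.
- **The two studies' estimates differ anyway.** A reader might infer that unequal covariate lists make them non-comparable. They already differ in how infection is established (self-report or clinical record) and in how controls are defined. A common list would not make them the same quantity, and differing lists alone do not make them incomparable.
- **The size is unknown.** It is tempting to express the bias as a share of the 0.2 SD in section 7.1. That difference goes with the 500 versus 500 design, which the synopsis and section 4.9 assign to the nested study, and the inputs to any such percentage would be assumed.
- **Study site.** A reader might take the remark in 5.1 about selected Health Boards as grounds for adjusting for site. It qualifies only the written approach after an SCI Diabetes search, not clinic-list screening.
- **An analysis plan will follow.** Section 7.2 promises one, and it may revise the list. But the protocol itself names the covariates of its primary analysis, so this is a stated choice and not one left open.

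Adjusting for SIMD after matching on it is ordinary practice, so the nested models are not at fault. None of these points explains why SIMD is left out of the cohort model.

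**Conclusion.** The point holds for SIMD. The protocol collects the means to derive it, uses it for matching and in both nested primary models, and omits it without explanation from the cohort primary model, where no matching is described. The infected-versus-control difference in current symptom score is therefore open to confounding that could be reduced with data already in hand. Whether it is materially biased, and in which direction, cannot be established from the protocol; the 0.005 to 0.10 SD range is illustrative only. The conclusion assumes that deprivation differs between the groups beyond what age, sex, ethnicity and type of diabetes explain, and that it relates to symptoms. The recruitment routes make the first plausible, and the protocol's own handling of SIMD suggests that it takes the second seriously. Diabetes duration is a worthwhile improvement, not an error.

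**What to change.** In section 7.2, add SIMD quintile to the covariates of the cohort primary comparison, so that it agrees with the nested models. Define the demographic panel once and refer to that definition in sections 4.10, 5.1, 6.2 and 7.2. Reconcile the description of the online study as matched in section 1 with the absence of a matching step.

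As an optional addition, include the diabetes-duration band. It describes a state that generally precedes infection, so adjusting for it should not remove part of the effect of infection, and it may stand in for complications, which the cohort has no clinical records to measure.

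The cost is a short wording change and no new data collection; the loss of precision is at most about 0.6% in residual SD under the assumptions above. The limitation to state is that SIMD derived from four postcode characters may be coarse, so residual confounding by deprivation may remain.
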